7.3 EFFICACY ASSESSMENTS

Studying the efficacy of PepCan and the schedule in which this protocol specifically outlines the clinical response (i.e., reduced cancer recurrence rate) of subjects is a secondary endpoint. Immune response will be evaluated as the tertiary endpoint, and microbial response will be assessed as the quaternary endpoint. This section includes a list and description of the procedures that will be conducted.

ASSESSMENT OF CLINICAL EFFICACY

Cancer recurrence rate will be compared for a 2-year period between the PepCan and placebo arms using Fisher's exact test.

COLLECTION OF BIOLOGICAL SPECIMEN AND URINE SPECIMEN

URINE SPECIMEN

A urine pregnancy test will be administered to subjects of childbearing potential at every visit and the results reviewed by the study team before injection.

ORAL WASH SPECIMEN

- 1. Oral wash specimens will be collected at Screening, Visit 5, Visit 7 and Visit 8.
- 2. Subjects will be asked to swish 10mL of mouthwash and spit into a cup.

BLOOD DRAW

- 1. Blood draw will be performed by a trained phlebotomist or other medical professional
- 2. CBC with differential on Visits Screen, 1, 3, 5, 6, 7, 8, 9
- 3. Chem 7 on Visits Screen, 1, 3, 5, 6, 7, 8, 9
- 4. LFTs on Visits Screen, 1, 3, 5, 6, 7, 8, 9
- 5. 8 rubber green top tubes on Visits 1, 5, 8, 9

STOOL SAMPLE

- 1. Stool samples will be collected with OMNIgene•GUT kit (ref. OMR-200) which includes a toilet accessory sheet, collection tube, and spatula.
- 2. Subjects will be given appropriate packing and shipping supplies to be sent back to UAMS at Visits Screen, 5, 7, and 8 to the following address:

Cancer Clinical Trials Office

[name]

[name]

3. Instructions will be given to the subject at each visit, but the full instructions for the kit can also be found at: http://www.dnagenotek.com/US/support/ciOMR200.html

FUTURE USE OF REMAINING SAMPLES

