7.6 QUESTIONNAIRES

DEMOGRAPHICS AND CONTACT INFORMATION FORM

The Demographics and Contact Information Form serves to collect information regarding patient name, date of birth, race, ethnicity, phone number, and email address. This form will be completed at the screening visit. The purpose of obtaining this information is to obtain updated patient demographic and contact information for the study.

SCREENING VISIT QUESTIONNAIRE

The Screening Visit Questionnaire serves to collect information regarding HPV vaccination status, recruitment, employment, education, dependents, sexual life, tobacco usage, and alcohol usage. The purpose of obtaining this information is to characterize the subject population and to identify variables that may be associated with vaccine response.

ORAL WASH ANTIBIOTIC USAGE QUESTIONNAIRE

The Oral Wash Antibiotic Usage Questionnaire serves to collect information regarding patient antibiotic usage within the last 30 days, mouthwash usage, and details for oral wash collection sample. The purpose of obtaining this information is to aid in the interpretation of microbiome data as antibiotics are known to drastically alter them.

STOOL SAMPLE ANTIBIOTIC USAGE QUESTIONNAIRE

The Stool Sample Antibiotic Usage Questionnaire serves to collect information regarding patient antibiotic usage within the last 30 days. The purpose of obtaining this information is to aid in the interpretation of microbiome data as antibiotics are known to drastically alter them.

VISIT 9 QUESTIONNAIRE

The Visit 9 Questionnaire serves to collect information regarding patient experience such at the end of study treatment. The purpose of obtaining this information is to improve retention.

RECURRENCE QUESTIONNAIRE

The Recurrence Questionnaire serves to collect information regarding patient experience such at the end of study treatment. The purpose of obtaining this information is to improve retention.

EARLY TERMINATION QUESTIONNAIRE

The Early Termination Questionnaire serves to collect information regarding reasons why patients are withdrawing their participation on study prior to completion of study treatment. The purpose of obtaining this information is to improve retention.

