8. STATISTICAL CONSIDERATIONS

8.1 DETERMINATION OF SAMPLE SIZE

The recurrence rate of head and neck cancer is 80% over 2 years (50 to 60% local recurrence and 20 to 30% distant recurrence [41]. In the Phase I trial of PepCan described above the overall histological regression rate of HSILs was 45% [36]. A reduced recurrence rate by the magnitude of 45% would reach 44%. Vaccinating 72 subjects in the PepCan arm and 24 subjects in the placebo arm would have 90% power at alpha of 5%, 2 tailed. Accounting for about 5% drop out rate, 75 subjects would be needed in the PepCan arm, and 25 subjects in the placebo arm.

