8.2 STATISTICAL ANALYSES

Subjects who received at least one dose of the vaccine will be included in safety assessments. Safety analyses will include summaries of the incidence of AEs using the NCI CTCAE Version 5.0 that occur during the study period regardless of causality. The AEs will be mostly descriptive initially. However, after unblinding at the completion of the study, rates of common side effects (occurring with 5% or more injections) will be compared between the PepCan and the placebo arms. Efficacy will be assessed by comparing cancer recurrence rate between the 2 arms. The expected number of head and neck cancer patients who achieve remission is 100 patients per year. For immunological assessments, the presence of new anti-HPV-16 E6 T-cell activity will be measured using CD3 ELISPOT assay, and its statistical significance will be assessed using a paired *t*-test. For analyses of immune cells such as Th1, Th2, Treg, and MDSCs, percentages before and after vaccination will also be assed using a two-tailed paired *t*-test. The frequencies between subjects who experience recurrence and those that do not in the PepCan arm will be compared using Wilcoxon rank-sum test. The diversity of gut microbiome will be assessed prior to

injection, and will be compared to that after injection using alpha diversity, beta diversity, and compositions at the phylum or family levels. These parameters will also be compared between subjects with and without recurrence with in the PepCan arm.

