9.2 STUDY DISCONTINUATION AND CLOSURE

Subjects are free to withdraw from participation in the study at any time upon request.

An investigator may discontinue a subject's participation from vaccination or from the study for the following reasons:

- Pregnancy
- Significant study intervention non-compliance
- Any subject experiencing a vaccine-related toxicity
- Disease progression, and/or unrelated health condition which requires discontinuation of the study intervention
- Any reason that the investigator feels it is not in the subject's best interest to continue

The sponsor may decide to stop the study at any point, for any reason.

INDIVIDUAL SUBJECT STOPPING RULES

Subjects who experience injection-induced/related serious dose limiting toxicities should be removed from the study treatment (vaccine) but will continue with assessments per the study calendar, including collection of study labs. Injection-induced serious toxicity will be defined (using CTCAE Version 5.0) as:

- Grade II or higher allergic reactions. Grade II is defined as "Oral intervention indicated". Grade III is defined as "Bronchospasm; hospitalization indicated for clinical sequelae; intravenous intervention indicated".
- Grade II or higher autoimmune reactions/disorders. Grade II is defined as "evidence of autoimmune reaction involving a non-essential organ or function (e.g., hypothyroidism)". Grade III is defined as "autoimmune reactions involving major organ (e.g., colitis, anemia, myocarditis, kidney)".
- Any Grade III or higher event.

If a subject becomes pregnant during her participation in the study, a medical monitor will determine whether or not she should be removed from the study. Medical records will be requested to determine the health of the mother and child.

For all other circumstances, the local site PI may determine whether or not a subject needs to be removed from the study. In either case written notification, documenting the reason for study suspension or termination, will be provided to the study subject, Investigator, ORRA, and local regulatory authorities. If a subject withdraws or is withdrawn, they will be asked to complete the Early Termination Questionnaire. Withdrawn subjects will not be replaced.

STUDY STOPPING RULES

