- Before a subject is deemed lost to follow-up, the investigator or designee will make every effort to regain contact with the subject (where possible, 3 telephone calls and, if necessary, a certified letter to the subject's last known mailing address or local equivalent methods). These contact attempts will be documented in the subject's medical record or study file.
- Should the subject continue to be unreachable, he or she will be considered to have withdrawn from the study with a primary reason of lost to follow-up.

TRAVEL STIPENDS

Travel stipends will be available based on institutional guidelines

CONFIDENTIALITY AND PRIVACY

Subject confidentiality and privacy is strictly held in trust by the participating investigators, their staff, and the sponsor(s). This confidentiality is extended to cover testing of biological samples and genetic tests in addition to the clinical information relating to subjects. Therefore, the study protocol, documentation, data, and all other information generated will be held in strict confidence. No information concerning the study or the data will be released to any unauthorized third party without prior written approval of the sponsor.

All study related documents will be kept in accordance with local institutional practices.

All research activities will be conducted in as private a setting as possible.

The study monitor, other authorized representatives of the sponsor, representatives of the IRB, regulatory agencies or pharmaceutical company supplying study product may inspect all documents and records required to be maintained by the investigator, including but not limited to, medical records (office, clinic, or hospital) and pharmacy records for the subjects in this study. The clinical study site will permit access to such records.

The study subject's contact information will be securely stored at each clinical site for internal use during the study. At the end of the study, all records will continue to be kept in a secure location for as long a period as dictated by the reviewing IRB, Institutional policies, or sponsor requirements.

KEY ROLES AND STUDY GOVERNANCE

UAMS Principal Investigator (PI)	Medical Monitor
[name]	[name]
University of Arkansas for Medical Sciences	University of Arkansas for Medical Sciences
Winthrop P. Rockefeller Cancer Institute	Winthrop P. Rockefeller Cancer Institute
7th Floor	7th Floor
[name]	[name]
[name]	[name]

MONITORING

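### The 90% power in section 8.1 is that of an uncorrected chi-square test; the Fisher's exact test named in 7.3 has 87%, and no rule says how unknown 2-year status enters its table

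*Combined protocol and SAP*

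**What the plan says.** Section 7.3 names the efficacy analysis: "Cancer recurrence rate will be compared for a 2-year period between the PepCan and placebo arms using Fisher's exact test". Section 8.2 adds only "Efficacy will be assessed by comparing cancer recurrence rate between the 2 arms".

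Section 8.1 sizes the trial on this comparison, assuming 80% recurrence on placebo and 44% on PepCan: "Vaccinating 72 subjects in the PepCan arm and 24 subjects in the placebo arm would have 90% power at alpha of 5%, 2 tailed". It then allows for loss: "Accounting for about 5% drop out rate, 75 subjects would be needed in the PepCan arm, and 25 subjects in the placebo arm".

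The one analysis set that section 8.2 defines is for safety: "Subjects who received at least one dose of the vaccine will be included in safety assessments". Section 9.2 says "Withdrawn subjects will not be replaced", and of a subject who stays unreachable, "he or she will be considered to have withdrawn from the study with a primary reason of lost to follow-up". Section 7.6 describes the form completed on withdrawal: "The Early Termination Questionnaire serves to collect information regarding reasons why patients are withdrawing their participation on study prior to completion of study treatment".

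Two further passages matter. Section 5.5 puts a subject in the recurrence group when a study physician judges recurrence from clinical and/or radiological evidence. Section 3 has recurrence assessed at all ten visits.

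**The concern.** There are two separate gaps.

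First, Fisher's exact test is conservative in samples of this size, so a power figure from a normal approximation does not carry over to it. If 90% comes from another test, section 8.1 overstates the chance that the planned analysis detects the assumed effect.

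Second, Fisher's test needs a yes or no for everyone in the table. The plan expects dropout and does not replace it, yet no section says whether subjects of unknown 2-year status are left out, counted as recurrence-free or counted as recurrences. The withdrawal form is described as recording reasons, not disease status. Without a written rule, the choice can be made after unblinding, when its effect on the p-value is visible. Death without recurrence is also not addressed explicitly, although section 5.5 largely settles it.

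**Working it through.** **Inputs from section 8.1.** Placebo 0.80; PepCan 0.80 × (1 − 0.45) = 0.44; difference 0.36; 72 and 24 evaluable; two-sided 5%; dropout about 5%; 75 and 25 enrolled.

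**Step 1: reproduce the stated power.** Pooled, uncorrected formula: power = Φ[(Δ − 1.96 × SE0) / SE1].
- Pooled proportion: (72 × 0.44 + 24 × 0.80) / 96 = 50.88 / 96 = 0.53.
- SE0 = √[0.53 × 0.47 × (1/72 + 1/24)] = 0.1176.
- SE1 = √[0.44 × 0.56/72 + 0.80 × 0.20/24] = 0.1004.
- Power = Φ[(0.36 − 1.96 × 0.1176) / 0.1004] = Φ(1.29) = 0.901.

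The plan's 90% is reproduced. Exact enumeration of the uncorrected chi-square test at 72/24 also gives 0.901.

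**Step 2: power of the named test.** Sum the binomial probabilities of all tables in which Fisher's two-sided p is at most 0.05.

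| PepCan/placebo | Fisher power |
|---|---|
| 72/24 | 0.870 |
| 75/25 | 0.890 |
| 78/26 | 0.912 |

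78/26 is the smallest 3:1 size at which Fisher's test reaches 90%. The 72/24 row is the one that matches section 8.1's own logic, in which dropouts leave the denominator. The 75/25 row applies only if nobody is lost.

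**Step 3: can the missing rule change a result at the planned loss?** Take 3 PepCan and 1 placebo subject lost, leaving 72/24 known, with 17/24 placebo and 33/72 PepCan recurrences.

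| Lost subjects | Placebo vs PepCan | Fisher p |
|---|---|---|
| Excluded | 17/24 vs 33/72 | 0.037 |
| Counted recurrence-free | 17/25 vs 33/75 | 0.063 |
| Counted as recurrences | 18/25 vs 36/75 | 0.041 |
| Worst case for PepCan | 17/25 vs 36/75 | 0.107 |

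That example is near the boundary. At about the planned rates the choice matters less until loss grows:

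| Lost (PepCan + placebo) | Known: placebo vs PepCan | p excluded | p worst case |
|---|---|---|---|
| 4 + 1 (5%) | 19/24 vs 31/71 | 0.004 | 0.012 |
| 8 + 2 (10%) | 18/23 vs 29/67 | 0.004 | 0.064 |
| 15 + 5 (20%) | 16/20 vs 26/60 | 0.005 | 0.49 |

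The 10% and 20% rows are assumptions; the documents give only about 5%.

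**Step 4: average effect, and what cumulative incidence adds.** Simulation of 25/75 subjects with constant hazards giving 80% and 44% at 24 months, independent dropout and recurrence dated to the next scheduled visit.
- *Power at 5% dropout, no deaths:* Fisher 0.86–0.87; uncorrected chi-square on the same table 0.90–0.91; cumulative incidence at Visit 9 with a log-log test 0.915–0.919. Of the gain of about 5 points, about 3.5 are Fisher's conservatism.
- *Estimates at 5% dropout, unknowns excluded:* 79.3%/43.3% (placebo/PepCan) against a truth by Visit 9 of 78.7%/42.7%. Each arm shifts by 0.6 point and the difference stays at 36.0 points.
- *Deaths (assumed 10% hazard over 2 years):* cumulative incidence 75.7%/40.8%; the Fisher table with deaths as non-recurrence 76.1%/41.2%.
- *No true effect, equal dropout of 5% or 20%:* Fisher rejects in 3.4–4.7% of trials, cumulative incidence in 4.3–5.9%.

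**The case against.** The strongest case on the other side has four parts.

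*Efficacy is secondary and the shortfall is about 3 points.* Both are true. They limit the weight of the point, but section 8.1 still uses this comparison to justify 100 subjects, and the figure does not belong to the named test.

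*Section 5.5 already decides deaths.* Largely so. Only a subject judged by a physician to have recurred enters the recurrence group, so a death without such evidence reads as non-recurrence. One explicit sentence is enough.

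*Dropout should be low.* Sections 7.2 and 9.2 keep subjects who stop injections for toxicity in the assessments, so stopping vaccine is not by itself loss. That supports the small average effect. It does not supply a rule for those who are lost.

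*Cumulative incidence has its own weakness.* A reader might infer that it should replace Fisher's test because it handles unknown status. The documents do not support that. Censoring assumes loss unrelated to recurrence. In a deliberately extreme simulation (no true effect, 5% independent dropout on placebo, 20% dropout on PepCan made up only of subjects about to recur), Fisher's test excluding unknowns rejected in 6.6% of trials and cumulative incidence in 12.7% at 80% recurrence; at 60% recurrence the figures were 10.8% and 18.3%. Replacement would also trade an exact test for an approximate one with 25 placebo subjects. This objection stands, so cumulative incidence belongs as a sensitivity analysis.

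**Conclusion.** The power statement in section 8.1 is wrong for the test in section 7.3: about 87%, not 90%, at 72/24. This is exact arithmetic on the plan's own inputs. It does not show that the sample size is inadequate: 87% to 89% remains reasonable power under the stated assumptions, and the fault is the mismatch between figure and test.

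The rule for unknown 2-year status is missing. At the documented 5% dropout, assumed independent of recurrence, the harm is small on average: about half a point of upward shift per arm and little change in the difference. The risk is an unwritten choice that can move a borderline result across 0.05.

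A reader might also infer inflated type I error. The documents do not support that. Exclusion, the handling that section 8.1 implies, stays at or below 4.7% with equal independent dropout. Clear inflation (9.7–13.1% at 80% recurrence in both arms) appeared when lost subjects were counted as recurrence-free and dropout was 30% in one arm and 5% in the other. The plan states neither condition.

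**What to change.** Before unblinding:

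1. **Section 8.1.** State about 87% power for Fisher's exact test at 72/24 (89.0% if all 75/25 have known status), or name the test that gives 90%.
2. **Sections 7.3 and 8.2, if Fisher's test stays the main analysis.** State that subjects of unknown 2-year status are excluded, as the inflation from 72/24 to 75/25 implies, and that death without evidence of recurrence counts as non-recurrence, consistent with section 5.5.
3. **Sensitivity analyses.** Pre-specify cumulative incidence of recurrence at Visit 9, with death as a competing event, withdrawn or lost subjects censored at the last disease assessment, a log-log test and a 95% confidence interval. Read it on the scheduled-visit scale: Visit 9 falls nominally at 63 days + 21 months = 23.1 months, so a calendar 24-month reading would often lie beyond the last assessment. Add a worst-case analysis for informative loss.
4. **Data.** Record the dates of recurrence, last disease assessment and death. The eCRF is not among the documents, so some of these may already be there.

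The cost is a protocol amendment with IRB approval, standard programming and up to three dates. The stated power becomes slightly less favourable. No visit is added, since section 3 already has recurrence assessed at every visit. However, no physical examination is scheduled at Visits 1 to 4, so early recurrence-free time may rest on interview.

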4. STUDY DESIGN

4.1 OVERALL DESIGN

This is a Phase I/II randomized, double-blind, placebo controlled, multi-site study of PepCan. It is designed to show the safety and efficacy of a 7-dose regimen of PepCan over a two-year period in terms of reducing cancer recurrence rate by comparing the recurrence rates between the PepCan and the placebo arm. The ratio of the number of subjects who will receive PepCan versus placebo will be 3:1. The study randomization schematic will be constructed by the Study Statistician. Subjects will be randomized in a 3:1 ratio to PepCan or placebo, and randomization will be done in a book form by Research Pharmacy. Up to 150 subjects will be for screened until 100 subjects are eligible for injection.

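### Fisher's exact test for 2-year recurrence is valid but spends only about 3.3–3.8% of the 5% error; Boschloo's test ordered by the two-sided Fisher p value recovers 0.7–2.7 points of power at the design rates

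*Combined protocol and SAP*

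**What the plan says.** Section 7.3 gives the efficacy test: "Cancer recurrence rate will be compared for a 2-year period between the PepCan and placebo arms using Fisher's exact test". Section 8.2 names no test for recurrence and says only: "Efficacy will be assessed by comparing cancer recurrence rate between the 2 arms".

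Section 8.1 supplies the design figures. Placebo: "The recurrence rate of head and neck cancer is 80% over 2 years". PepCan: "A reduced recurrence rate by the magnitude of 45% would reach 44"%, since 80% × (1 − 0.45) = 44%. Size and error: "Vaccinating 72 subjects in the PepCan arm and 24 subjects in the placebo arm would have 90% power at alpha of 5%, 2 tailed". Allowance for loss: "Accounting for about 5% drop out rate, 75 subjects would be needed in the PepCan arm, and 25 subjects in the placebo arm". Section 4.1 sets the allocation: "Subjects will be randomized in a 3:1 ratio to PepCan or placebo".

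Sections 3 and 7.3 make recurrence a secondary endpoint; safety is primary. The protocol does not say why Fisher's test was preferred to another exact test.

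**The concern.** Fisher's test conditions on the total number of recurrences in the two arms. The protocol fixes the arm sizes and not that total. With about 24 placebo subjects the conditional distribution moves in coarse steps, so the rejection region usually stops well short of 5%. Part of the error rate that section 8.1 allows is then never used, and power is lost with it.

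Recurrence is a secondary endpoint, but it is the outcome on which the trial was sized, and the placebo arm is small. Under section 9.2 withdrawn subjects are not replaced, so the analysed table may be smaller still. If another exact test gives the same 5% guarantee and rejects more often, the plan gives up power that costs no subjects to recover.

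**Working it through.** **Inputs (section 8.1, except the ratio from 4.1).** Placebo 80%, PepCan 44%, two-sided 5%, ratio 3:1, 72 + 24 evaluable, 75 + 25 enrolled. A third case, 71 + 23, applies 5% loss to the enrolled numbers and rounds down: 75 × 0.95 = 71.25 and 25 × 0.95 = 23.75.

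**1. The plan's own figure.** The usual normal-approximation formula without continuity correction uses the pooled rate (0.80 + 3 × 0.44)/4 = 0.53. Then

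n(placebo) = [1.96 √(0.53 × 0.47 × 4/3) + 1.2816 √(0.80 × 0.20 + 0.44 × 0.56/3)]² / 0.36² = (1.1295 + 0.6306)² / 0.1296 = 23.9.

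This rounds to 24 placebo and 72 PepCan, with approximate power 90.1%. The stated sizes reproduce, but from a formula that is not Fisher's test.

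**2. True size of Fisher's test.** List every 2×2 table (x recurrences of n₁ on PepCan, y of n₂ on placebo). Compute the two-sided Fisher p value as the summed conditional probability of all tables no more likely than the one observed. For a common rate π,

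size(π) = Σ Bin(x; n₁, π) · Bin(y; n₂, π) over tables with p ≤ 0.05.

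**3. Boschloo's test on the same p value.** Find the largest cut-off c on that Fisher p value whose maximum size over all π is at most 5%. Fisher's test at 0.05 already has maximum size below 5%, so c is at least 0.05. The Boschloo region therefore contains the Fisher region, and power cannot be lower at any pair of rates.

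| | 72 + 24 | 75 + 25 | 71 + 23 |
|---|---|---|---|
| Fisher size, π from 20% to 80% | 3.3–3.8% | 3.4–3.8% | 3.1–4.0% |
| Fisher maximum size | 3.8% | 3.8% | 4.0% |
| Boschloo cut-off c | 0.0593 | 0.0624 | 0.0554 |
| Boschloo maximum size | 4.94% | 5.00% (just under) | 4.78% |
| Extra tables rejected | 28 | 32 | 22 |

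At common rates of 10% or 90%, Fisher's size falls to about 2.6–2.7% in the first two cases.

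**4. Power at 80% v 44%**, summing Bin(x; n₁, 0.44) · Bin(y; n₂, 0.80) over each rejection region:

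| | Fisher | Boschloo | Gain (points) |
|---|---|---|---|
| 72 + 24 | 87.0% | 89.7% | 2.7 |
| 75 + 25 | 89.0% | 89.6% | 0.7 |
| 71 + 23 | 84.8% | 88.5% | 3.7 |

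(Gains are taken before rounding.)

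**5. Lower placebo recurrence (assumption)**, keeping the 45% relative reduction, so PepCan rate = 0.55 × placebo rate. Gain in points:

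| Placebo rate | 72 + 24 | 75 + 25 |
|---|---|---|
| 75% | 3.9 | 0.6 |
| 70% | 5.6 | 1.5 |
| 65% | 7.0 | 3.4 |
| 60% | 6.9 | 5.1 |
| 55% | 5.1 | 5.2 |
| 50% | 3.0 | 3.9 |
| 40% | 1.9 | 3.6 |
| 30% | 1.9 | 2.6 |
| 20% | 1.5 | 1.7 |

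At 60% v 33%, for example, power goes from 57.1% to 64.0% (72 + 24) and from 59.9% to 65.0% (75 + 25). At 71 + 23 the gain is about 3 points at 60% v 33% and about 0.1 at 20% v 11%.

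**6. The version matters.** A two-sided Boschloo test that doubles the smaller one-sided p value fails to reject 4 tables that Fisher's test rejects, at both 72 + 24 and 75 + 25. At 20% v 11% its power is 15.8% against Fisher's 16.9% (72 + 24) and 17.3% against 17.5% (75 + 25). At 80% v 44% it does beat Fisher's test (89.6% and 91.0%), but it does not dominate it.

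**The case against.** Fisher's test is a legitimate choice. It holds the error at or below 5%, both overall and conditionally on the observed total. In a randomized trial there is an argument for conditioning: if treatment has no effect on any subject, the total number of recurrences is the same under every allocation. It is also familiar to readers. The endpoint is secondary, and at the enrolled 75 + 25 and the design rates the gain is only 0.7 points.

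All of this stands as a reason to treat the point as an improvement. It does not remove it. Section 8.1 asks for a two-tailed 5% and no conditional guarantee, and anyone who prefers the conditional result can still have it as a sensitivity analysis.

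Three stronger readings are tempting. A reader might infer that the efficacy analysis is invalid; it is not, because Fisher's test errs on the safe side. A reader might infer that the loss keeps growing as placebo recurrence falls below 80%; at 72 + 24 it peaks near 60–70% and then shrinks. And a reader might infer that any test called Boschloo's is at least as powerful as Fisher's; the doubled one-sided version is not.

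**Conclusion.** The point holds as a loss of efficiency. At 72 + 24, Fisher's test gives 87.0% power at the plan's rates; the dominating Boschloo test gives 89.7%, close to the stated 90%. At 75 + 25 the difference is small, and at 71 + 23 it is 3.7 points. Larger gains of 5–7 points at 72 + 24 need a placebo rate of about 55–70%, which the plan does not assume.

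The figures rest on independent binomial outcomes in the two arms, every analysed subject classified at 2 years, and tables ordered by the two-sided minimum-likelihood Fisher p value. The conclusion that this Boschloo test is never less powerful does not depend on the assumed rates; the size of the gain does.

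**What to change.** Before unblinding, amend section 7.3 so that 2-year recurrence is compared by Boschloo's exact test, two-sided at 5%, with the two-sided minimum-likelihood Fisher p value stated as the ordering statistic. Add the same sentence to section 8.2, which at present names no test for recurrence. Keep Fisher's p value as a sensitivity result. If an exact unconditional confidence interval for the risk difference is reported, state its ordering statistic as well, because an interval built on a different ordering need not agree with the test.

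The cost is a small protocol amendment, which needs IRB approval under the Statement of Compliance, and a test less familiar to readers. The analyst must also check that the software uses the stated two-sided version. No extra subjects, visits or data are needed. Timing matters: a change of test made after unblinding could look driven by the results.

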3. OBJECTIVES AND ENDPOINTS

OBJECTIVES	ENDPOINTS	JUSTIFICATION FOR ENDPOINTS
PRIMARY		
Determine the safety of a	Careful monitoring of adverse events	Investigators will use NCI CTCAE
7-injection scheduling of	(AEs) at all ten (10) visits (2 years)	Version 5.0 to assess AEs and
PepCan regimen.	based on NCI CTCAE Version 5.0.	evaluate the safety of PepCan.
SECONDARY		
Determine the efficacy of	The absence of recurrence will be	The goal of PepCan vaccine is to
a 7-injection PepCan	assessed at all ten (10) visits (2 years).	reduce recurrence of head and
regimen.	Recurrence rates will be compared	neck cancer.
	between the PepCan and placebo arms.	
TERTIARY		
Determine immunological	T-cell (ELISPOT assay) and immune	Immunological responses are
responses to a 7-injection	regulatory cell responses (FACS	important in preventing cancer
PepCan regimen.	analysis) at Visits 1, 5, 8, and 9 will be	recurrence.
	assessed before and after vaccination.	
EXPLORATORY		
Compare the profile of	DNA sequencing methods will be	Diversity of gut microbiome is
gut and oral microbiome	utilized. Stool samples will be analyzed	now recognized to be associated
before and after PepCan	after Screening Visit, and Visits 5, 7, and	with favorable response to
regimen.	8. Oral wash samples will be analyzed at	cancer immunotherapy [27].
	Screening Visit, and Visits 5, 7, and 8.	

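### The only efficacy test, Fisher's exact test on 2-year recurrence, has 87.0% power rather than the stated 90% and ignores when recurrence occurred; a pre-specified time-to-recurrence test robust to a delayed effect would gain a few points at little cost

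*Combined protocol and SAP*

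**What the plan says.** Section 7.3 states that "Cancer recurrence rate will be compared for a 2-year period between the PepCan and placebo arms using Fisher's exact test". Section 8.2 names no test for this comparison: "Efficacy will be assessed by comparing cancer recurrence rate between the 2 arms". No time-to-recurrence analysis (Kaplan-Meier, log-rank, Cox) and no censoring rule appears anywhere.

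The secondary endpoint in section 3 is to be "assessed at all ten (10) visits (2 years"). Section 5.5 has a study physician determine recurrence and ends study injections at that point.

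The sample size in section 8.1 rests on this endpoint. Its control assumption is: "The recurrence rate of head and neck cancer is 80% over 2 years". A relative reduction of 45% is then applied to obtain the PepCan figure, 0.80 x 0.55 = 0.44. On power, the section claims: "Vaccinating 72 subjects in the PepCan arm and 24 subjects in the placebo arm would have 90% power at alpha of 5%, 2 tailed". It then adds, for enrolment: "Accounting for about 5% drop out rate, 75 subjects would be needed in the PepCan arm, and 25 subjects in the placebo arm". Section 4.1 fixes the allocation: "Subjects will be randomized in a 3:1 ratio to PepCan or placebo".

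**The concern.** Any test on the 2x2 table of arm by recurrence treats a recurrence at month 4 like one at month 23. With only 24 or 25 placebo subjects, dates that the trial will largely hold anyway could add power without adding subjects. Fisher's test is also conservative, so its true power lies below the figure in 8.1. At stake is the chance of detecting a reduction in recurrence. That objective is secondary to safety, but it is the one on which the whole trial is sized.

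**Working it through.** **Inputs.** From the documents: control recurrence 80%, PepCan 44%, 72 v 24 subjects, two-sided 5%, stated power 90% (8.1); follow-up of two years from first injection (1.1). Assumed, because the documents are silent: the shape of the hazards.

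**1. The stated 90%.** Uncorrected two-proportion formula:
- Pooled rate = (24 x 0.80 + 72 x 0.44)/96 = 50.88/96 = 0.53.
- Null SE = sqrt(0.53 x 0.47 x (1/72 + 1/24)) = 0.1176.
- Alternative SE = sqrt(0.44 x 0.56/72 + 0.80 x 0.20/24) = 0.1004.
- z = (0.36 - 1.96 x 0.1176)/0.1004 = 1.29, giving power 90.1%.

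The plan's figure is reproduced, but it belongs to an uncorrected chi-square test and not to Fisher's test.

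**2. The planned test.** Power = sum over all (x, y) of Bin(x; 72, 0.44) x Bin(y; 24, 0.80) x I{Fisher p <= 0.05}. Full enumeration gives **87.0%** at 72/24 and 89.0% at the enrolled 75/25. At 60% v 33% (the same 45% relative reduction) it gives 57.1%. The largest true size at 72/24 is 3.8%.

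**3. Proportional hazards, asymptotic log-rank.** Implied HR = ln(1 - 0.44)/ln(1 - 0.80) = 0.580/1.609 = 0.36. Simulated log-rank power is 93.8%, so the gain is 93.8 - 87.0 = 6.8 points. The split is:
- Fisher's conservatism: a size-corrected yes/no test (Boschloo type) has 89.7% and the chi-square 90.1%, so 2.7 to 3.1 points.
- Timing: 93.8 - 89.7 = 4.1 or 93.8 - 90.1 = 3.7 points. With the log-rank held to Fisher's actual size, 91.3 - 87.0 = 4.3 points.

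So about 3 of the 7 points are conservatism and about 4 are timing.

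Cross-check by the Schoenfeld formula: 50.88 events, z = 1.021 x sqrt(50.88 x 0.75 x 0.25) - 1.96 = 1.19, power 88.4%. The formula understates simulated power here (3:1 allocation, large effect).

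**4. Permutation p-values.** Simulated null size of the asymptotic log-rank and maximum tests ranged up to 5.8%, so both were recalculated with permutation of arm. The maximum test takes the larger absolute value of the log-rank statistic and the Fleming-Harrington (0,1) statistic, whose weight 1 - S(t-) favours late differences. Monte Carlo error is about 0.4 points with 5,000 simulated trials.

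| Scenario, 72 v 24 | Fisher | Log-rank | Maximum test |
|---|---|---|---|
| 80% v 44%, proportional hazards | 87.0% | 91-93% | 89-91% |
| 60% v 33%, proportional hazards | 57.1% | 66-67% | 64% |
| 80% v 44%, 3-month delay | about 87% | 85-86% | 90-96% (3 to 6 months) |
| 80% v 44%, 6-month delay | about 87% | 74-80% | as above |

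The design-case ranges include continuous dates (log-rank 92.5%, maximum 91.2%) and dates known only at the five examination visits (91.4%, 88.9%).

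**5. What the delay scenarios assume.** The 2-year rates are held at 80% and 44%, so the effect after the delay must be stronger. With a 3-month delay, the PepCan cumulative hazard is 1.609 x 3/24 = 0.201 by month 3, leaving 0.379 over 21 months. The later HR is (0.379/21)/(1.609/24) = 0.27. With a 6-month delay, 0.402 accrues first, leaving 0.177 over 18 months, and the later HR is 0.15.

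**The case against.** The plan asks about the 2-year proportion, sizes the trial on 2-year proportions, and uses a test that is valid for them. Citing no guideline for the 2-year cut is not a defect. Efficacy is secondary. At the enrolled 75/25, if nobody is lost, Fisher is one point short of 90%. All of this stands, and it makes the point an inexpensive improvement rather than an error that invalidates the analysis.

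The power argument can also be pressed. A less conservative yes/no test has 89.7-90.1% at the design rates and 64-65% at 60% v 33%, so under proportional hazards the maximum test gains essentially nothing over it, and with examination-visit dating it falls just short. That also stands. The advantage of the maximum test over a better yes/no test lies in the delayed-effect scenarios.

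A reader might infer three stronger things that the documents do not support:
- **That discarding the dates costs the whole Fisher-to-log-rank gap**, about 7 points at the design rates and about 13 (57.1% to 69.9%, asymptotic) at 60% v 33%. Part of each gap is Fisher's conservatism, and the figures require proportional hazards, which the documents nowhere state.
- **That a log-rank test is simply better.** Section 2.3 describes a vaccine that works by building an immune response, and the first four injections span nine weeks, so a delayed effect is plausible. The advantage is then lost or reversed.
- **That exact timing is available for everyone.** Section 3 has assessment at all visits, but the schedule in 11.1 places physical examinations only at screening and Visits 5 to 9, with six-month gaps at the end, and lists no imaging.

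**Conclusion.** The point holds in a limited form. The named test has 87.0% power at 72/24, 3 points below the stated 90%, and uses no information on timing. At the design rates a permutation log-rank gains about 4 to 6 points if hazards are proportional, and nothing or less if the effect is delayed by about 3 months or more. The permutation maximum test gains about 2 to 4 points under proportional hazards, about 7 at 60% v 33%, and about 3 to 9 with delays of 3 to 6 months. It beat Fisher in every scenario run. It does not guarantee the stated 90%: with dates known only at examination visits and proportional hazards it has 88.9%. The size of the gain rests on assumed hazard shapes, with the 2-year rates held at the plan's values in the delay cases. The 87.0% rests only on the plan's own inputs.

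**What to change.** Before unblinding:

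- In 7.3 and 8.2, pre-specify one test of time from first injection to recurrence: the maximum of the log-rank and Fleming-Harrington (0,1) statistics, two-sided 5%, with the p-value from permutation of arm. Choose it over the plain log-rank because a delayed effect is plausible for a vaccine.
- Censor recurrence-free subjects at their last disease assessment, and state how death without recurrence is handled.
- Keep the 2-year recurrence proportions and their difference with a 95% CI as the reported effect, so the 2-year question is still answered.
- Record the date of recurrence on the eCRF.
- Restate the power in 8.1 for the chosen test, by simulation rather than the Schoenfeld formula. If Fisher is kept, state 87%.

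Cost: wording in three sections and one date field, with no added subjects, visits or procedures. Downsides: the test addresses the whole 2-year course rather than the 2-year point alone; dates will be coarse because examinations after screening fall only at Visits 5 to 9; and the maximum test gives up about 2 points against the log-rank if hazards are in fact proportional.
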